## 8.3 Safety

### 8.3.1 Physical Examination

Physical examination must be conducted by the Investigator.

A complete physical examination will include head, ears, eyes, nose, mouth, skin, cardiovascular and lung examinations, lymph nodes, gastrointestinal, musculoskeletal, and neurological systems. The limited physical examination will be focused on general appearance, the cardiovascular system as well as towards patient reported symptoms.

Any new clinically significant abnormal findings or worsening of conditions previously recorded as medical history should be documented in the source documents and reported in the eCRF as AE.

### 8.3.2 Pitting edema assessment

At each visit, an assessment of pitting edema will be performed.

The pitting edema will be assessed following this procedure:

- Place your index finger over the patient's tibia, 10 cm above the lateral malleolus
- Exert pressure for 5 seconds
- Any depression that does not resume its original contour almost immediately is a sign of pitting edema

If the presence of pitting edema is confirmed, the following scale should be used to grade it.

**Table 3. Pitting edema scale**

Grade	Physical Characteristics
1+	No visible change in shape of the extremity

	Pitting $\leq$ 2 mm Pit disappears rapidly
2+	No marked change in the shape of the extremity 2 mm $<$ pitting $\leq$ 5 mm Pit usually disappears in 10-15 seconds
3+	Noticeable swollen extremity 5 mm $<$ pitting $\leq$ 10 mm Pit may persist for about a minute
4+	Very swollen and distorted extremity Very deep pit $>$ 10 mm Pit may persist 2 – 5 minutes

The presence or absence of edema will be recorded at each visit (Yes/No). If there is a pitting edema, a grade will be recorded for the edema according to the pitting edema scale.

### 8.3.3 Vital Signs and Body Measurements

Body measurements will be taken, before vital signs measurement. Weight should be measured with a scale having an appropriate resolution. The scale should be placed on a stable and flat surface. Patients are to be weighed in similar attire (only light clothing) and without shoes at each visit. Height will be recorded only during Screening Period. Waist and hip circumferences will be measured at each visit as planned in *Table 1*. All these data have to be recorded in the source documents and reported in the eCRF

One HR measurement will be taken after the patient has been resting in supine or sitting position for at least 10 minutes and before blood samples are taken. The HR measurement will be followed by 3 BP measurements, using a standardized cuff adapted to the size of the patient's arm. BP readings will be taken with patients comfortably in a supine or sitting position with the arms raised to the level of the heart and in a supported position. All readings should be recorded as accurately as possible and the same BP device and the same patient's arm (preferentially the left arm) should be used for all assessments for a given patient.

All 3 readings have to be recorded in the source documents and reported in the eCRF. For analysis, the average of the 3 BP readings will be used.

Any new clinically significant abnormal findings or worsening of conditions previously recorded as medical history should be documented in the source documents and reported in the eCRF as AE.

### 8.3.4 Patient Diary

Patient diary will be dispensed according to *Table 1*.

Patients will be asked to report their IMP intakes (date + dose + time). Any new AE or concomitant medications should be reported by the patient on the diary.

At each visit, the Investigator will review the patient diary dispensed at the previous visit. The review will be documented in the source documents and the Investigator will have to sign and date the previous patient diary and keep it in the patient file. At each visit, except Week 3 (V2) where no IMP/patient diary dispensation occurs, the appropriate data have to be reported in the eCRF.

#### 8.3.5 *Supine 12-Lead electrocardiogram (ECG)*

A 12-lead ECG (I, II, III, aVR, aVL, aVF, V1-V6) will be performed at the visits shown in the Visit Schedule Chart in *Table 1* after the patient has been lying down resting for at least 10 minutes. Standard 12-lead digital ECGs will be recorded as single measurement. The ECG printout or electronic record will be evaluated by the Investigator and reported as “Normal” or “Abnormal” in the source documents and in the eCRF. If the ECG is evaluated as “Abnormal”, the Investigator should document in the source documents as well as in the eCRF, the specific abnormality and if this abnormality is “clinically significant” or “not clinically significant”. ECG printouts or electronic record will include date, time, patient number, and date/signature of the Investigator who reviewed the ECG. The ECG printouts or electronic records will be kept in the patient file.

Any new clinically significant findings or worsening of abnormalities previously recorded as Medical History on the ECG will be reported as AEs, and followed up and/or treated locally until the AE has resolved or the condition has stabilized.

#### 8.3.6 *Laboratory Assessments*

All laboratory measurements will be performed by a central laboratory using samples collected at the visits shown in the Visit Schedule Chart in *Table 1*. However, if judged necessary for the safety of the patients, the Investigator or POXEL may request unscheduled central laboratory assessments.

Blood samples will be collected, handled and stored according to the instructions described in the central laboratory manual.

A list of normal reference ranges will be provided by the central laboratory to POXEL and the Investigators before the study start. Any change in the normal reference ranges during the study will be forwarded by the central laboratory to POXEL and the Investigators, who will have to keep it in the Trial Master File (TMF) and respectively, in the Investigator Site File (ISF).

Central laboratory reports must be reviewed by the Investigator as soon as received. Each parameter must be assessed by the Investigator and the clinical significance of the abnormal

parameters must be documented. To confirm the review, the Investigator will have to sign and date the report and keep it in the patient file.

Any new clinically significant findings or worsening of laboratory abnormalities previously recorded as Medical History will be reported as AEs, and followed up and/or treated locally until the AE has resolved or the condition has stabilized. The CTCAE criteria, version 5.0, will be used to determine severity.

The following panel will be evaluated.

*8.3.6.1 Standard Safety Laboratory Panel (Blood and Urine)*

Hematology	Biochemistry	Urinalysis
Erythrocytes	Blood Urea Nitrogen	pH
Hemoglobin	Creatinine	Specific gravity
Hematocrit	Sodium	Protein
Red Blood Cell Morphology	Potassium	Glucose
Mean corpuscular volume	Chloride	Ketones
Mean corpuscular hemoglobin	Bicarbonate	Nitrites
Mean corpuscular hemoglobin concentration	Calcium	Urobilinogen
Leucocytes	Inorganic phosphate	Blood
Differential blood count (lymphocytes, monocytes, eosinophils, basophils, neutrophils/ absolute values and percentages should be given)	Total protein	Leucocytes
Thrombocytes	Albumin	If the dipstick result is abnormal: microscopic examination of the sediment for blood cells, cylinders, etc.
	Uric acid	
	Creatine phosphokinase	
	AST	
	ALT	
	GGT	
	TBL	
	ALP	
	hsCRP	
	TSH (during Screening Period only)	
Coagulation		
	aPTT	
	PT	
	INR	

*8.3.6.2 Viral Infection Screen Panel*

Hepatitis screening	HIV screening
HBsAg	Anti-HIV 1 and 2

anti-HCV, and in case of positive result, reflex test of  
HCV circulating RNA

#### 8.3.6.3 eGFR

eGFR will be calculated using the CKD-EPI formula, as follows [32]:

$$141 \times \min(Scr/\kappa, 1)^\alpha \times \max(Scr/\kappa, 1)^{-1.209} \times 0.993^{\text{Age}} \times 1.018 \text{ [if female]} \times 1.159 \text{ [if black]}$$

*Scr is serum creatinine (mg/dL),  $\kappa$  is 0.7 for females and 0.9 for males,  $\alpha$  is -0.329 for females and -0.411 for males, min indicates the minimum of  $Scr/\kappa$  or 1, and max indicates the maximum of  $Scr/\kappa$  or 1.*

#### 8.3.6.4 Serum and Urine Pregnancy Tests

For female patients of child-bearing potential only, a serum  $\beta$ -HCG test or a urine pregnancy test will be performed at the visits shown in the Visit Schedule Chart in *Table 1*.

Additional serum pregnancy testing should be performed whenever a menstrual cycle is missed or when pregnancy is otherwise suspected.

All pregnancy tests performed should be recorded in the source documents and reported in the eCRF.

If a pregnancy occurs during the study, refer to Section 8.3.10 *Pregnancy and In Utero Drug Exposure*.

#### 8.3.7 Bone mineral density

For postmenopausal women only, a standard DXA testing will be performed at the visits shown in the Visit Schedule Chart in *Table 1*.

If possible, all DXA testing for a given patient (historical testing or testing performed during Screening Period and Week 36 (V8-EoT)) should be performed at the same facility and using the same procedure.

DXA reports must be reviewed by the Investigator as soon as received. To confirm the review, the Investigator will need to sign and date the report and retain it in the patient file.

Any new clinically significant abnormal findings or worsening of conditions previously recorded in the medical history should be documented in the source documents and reported in the eCRF as an AE.

### 8.3.8 Adverse Events

Comprehensive assessment of AE experienced by the patient will be performed throughout the course of the study, from the time of the patient's ICF signature till the EoS (V9).

**It is of the utmost importance that all staff involved in the study is familiar with the content of this section. The Investigator is responsible for ensuring this.**

#### 8.3.8.1 Adverse Event Definitions

##### 8.3.8.1.1 Adverse Event (AE)

An AE is any untoward medical occurrence in a patient or clinical investigation patient administered a pharmaceutical product, which does not necessarily have a causal relationship with this treatment. An AE can therefore be any unfavorable and unintended sign (including an abnormal laboratory finding), symptom, or disease temporally associated with the use of a medicinal, whether or not considered related to the medicinal product.

The official definition also extends to AEs occurring under placebo or in a reference group receiving drug or non-drug therapy. Because of regulatory requirements, events occurring during drug-free and pre- and post-treatment periods should also be designated as AEs.

Therefore, safety surveillance applies to the time when the patient is included into the study (date of ICF signature) until the End-of-Study Visit (V9-EoS) performed two weeks after the End-of-Treatment Visit (V8-EoT).

In cases of surgical or diagnostic procedures, the condition/illness leading to such a procedure is considered as the AE rather than the procedure itself.

Adverse events will be assessed according to the Common Terminology Criteria for Adverse Events (CTCAE) version 5.0.

The Investigator is required to grade the severity/intensity of each AE according to CTCAE:

- CTCAE Grade 1: Mild; asymptomatic or mild symptoms; clinical or diagnostic observations only; intervention not indicated
- CTCAE Grade 2: Moderate; minimal, local or noninvasive intervention indicated; limiting age-appropriate instrumental activities of daily living (ADL)
- CTCAE Grade 3: Severe or medically significant but not immediately life-threatening; hospitalization or prolongation of hospitalization indicated; disabling; limiting self care ADL
- CTCAE Grade 4 (Life threatening): life-threatening consequences; urgent intervention indicated

- CTCAE Grade 5 (Death): death related to AE

#### 8.3.8.1.2 Adverse Drug Reaction (ADR)

All noxious and unintended responses to a medicinal product related to any dose should be considered ADR.

The phrase “responses to a medicinal product” means that a causal relationship between a medicinal product and an AE is at least a reasonable possibility e.g., the relationship cannot be ruled out.

The following judgments of the causality to IMP or study procedures will be used:

- Unrelated: IMP cannot be reasonably suspected, a reasonable explanation must be given
- Related: IMP can be reasonably suspected. AE could medically (pharmacologically/clinically) be attributed to the IMP.

#### 8.3.8.1.3 Serious Adverse Event (SAE)

A SAE is an AE occurring during any study phase (i.e., Screening, Treatment, Follow-up), that fulfills one or more of the following criteria:

- Results in death
- Is immediately life-threatening

NOTE: The term “life-threatening” in this definition refers to an event in which the patient is at risk of death at the time of the event; it does not refer to an event that hypothetically might cause death if it were more severe

- Requires inpatient hospitalization or prolongation of existing hospitalization

NOTE: Any hospital admission with at least one overnight stay will be considered an inpatient hospitalization. An emergency room visit without hospital admission will not be recorded as a SAE under this criterion, nor will hospitalization for a procedure scheduled or planned before signing of ICF. However, unexpected complications and/or prolongation of hospitalization that occur during elective surgery should be recorded as AE and assessed for seriousness.

Admission to the hospital for social or situational reasons (e.g. no place to stay, live too far away to come for hospital visits) will not be considered inpatient hospitalizations.

- Results in persistent or significant disability/incapacity
- Is a congenital anomaly/birth defect
- Is otherwise considered as medically important

Important medical events that may not result in death, be life-threatening, or require hospitalization may be considered as SAE when, based upon appropriate medical judgment, they may jeopardize

the patient or may require medical or surgical intervention to prevent one of the outcomes listed in this definition. Examples of such events include:

- allergic bronchospasm requiring intensive treatment in an emergency room or at home
- angioedema not severe enough to require intubation but requiring intravenous hydrocortisone treatment
- blood dyscrasias (e.g. neutropenia or anemia requiring blood transfusion, or convulsions that do not result in inpatient hospitalization)
- development of drug dependency or drug abuse

### **Events that do not meet the definition of an SAE**

Elective hospitalizations to simplify study treatment or study procedures are not considered as SAE. However, all events leading to unplanned hospitalizations or unplanned prolongation of an elective hospitalization (e.g. undesirable effects of any administered treatment) must be documented and reported as SAE.

### **Events not to be considered as AE/SAE**

Medical conditions present prior to ICF signature that do not worsen in severity or frequency during the study are defined as baseline medical conditions and are NOT to be considered as AEs.

### **Abnormal laboratory findings and other abnormal investigational findings**

Abnormal laboratory findings and other abnormal investigational findings (e.g. on an ECG tracing) should not be reported as AE unless they are associated with clinical signs and symptoms, lead to IMP discontinuation or are considered otherwise medically important by the Investigator. If an abnormality fulfills these criteria, the identified medical condition (e.g. anemia, pancreatitis) must be reported as the AE rather than the abnormal value itself.

NOTE: To ensure no confusion or misunderstanding of the difference between the terms "serious" and "severe," which are not synonymous, the following note of clarification is provided: The term "severe" is often used to describe the intensity (severity) of a specific event (as in mild, moderate, or severe myocardial infarction); the event itself, however, may be of relatively minor medical significance (such as severe headache). This is not the same as "serious," which is based on patient/event outcome or action criteria usually associated with events that pose a threat to a patient's life or functioning. Seriousness (not severity) serves as a guide for defining regulatory reporting obligations.

#### 8.3.8.1.4 Adverse Event of Special Interest (AESI)

An AE of Special Interest (AESI, serious or non-serious) is one of scientific and/or medical concern specific to the Sponsor's product or program, for which ongoing monitoring and rapid communication by the investigator to the Sponsor can be appropriate. Such an event might warrant further investigation in order to characterize and understand it. Depending on the nature of the event, rapid communication by the trial Sponsor to other parties (e.g., regulators) might also be warranted.

Even if non-serious, AESI are managed with the same process than SAE:

- notification to the Sponsor within 24h following investigator awareness
- case to be created and processed in the safety database (including narrative writing) by Safety Provider.

In this study, the following AEs are considered as AESI:

- Heart failure. In case of any event of heart failure, whatever the cause, patients should be referred to a cardiology specialist.
- Pitting edema. In case of occurrence of pitting edema with presence of other suspected signs and/or symptoms of heart failure, patients should be referred to a cardiology specialist.
- Bladder cancer
- Bone fracture
- Drug-induced liver injury (DILI)

**Below are specific recommendations for the management of elevated liver transaminases and/ or total bilirubin to detect and monitor a possible DILI, following FDA guidelines:**

- **For patients with normal liver transaminases and total bilirubin at baseline (Randomization Visit (V1)):**

If patients with normal baseline (Randomization Visit (V1)) liver indices develop new elevations of AST or ALT  $>3 \times$  ULN or TBL  $>2 \times$  ULN values during the study, repeat testing should be performed within 48 to 72 hours. Investigators should also ask the patient if he/she has symptoms.

If there are persistent elevations (ALT or AST  $>3 \times$  ULN or TBL  $>2 \times$  ULN) upon repeat testing, then close observation (as described below) should be implemented and discontinuation of drug should be considered.

Drug should be discontinued, and the patient followed until resolution of symptoms or signs in the following situations:

- ALT or AST  $>8 \times$  ULN
- ALT or AST  $>5 \times$  ULN for more than 2 weeks.

- ALT or AST  $>3 \times$  ULN and (TBL  $>2 \times$  ULN or INR  $>1.5$ , except for patients on anticoagulant treatment)
- ALT or AST  $>3 \times$  ULN with the appearance of fatigue, nausea, vomiting, right upper quadrant pain or tenderness, fever, rash, and/or eosinophilia ( $>5\%$ ).
- **For patients with elevations in liver transaminases or total bilirubin at baseline (Randomization Visit (V1)):**

If patients with abnormal baseline liver indices develop elevations of AST or ALT  $>2 \times$  baseline or TBL  $>2 \times$  baseline values during the study, repeat testing should be performed within 48 to 72 hours. Investigators should also ask to the patient if he/she has symptoms.

If there are persistent elevations (ALT or AST  $>2 \times$  baseline or TBL  $>2 \times$  baseline values) upon repeat testing, then close observation (as described below) should be implemented and discontinuation of drug should be considered.

Drug should be discontinued, and the patient followed until resolution of symptoms or signs in the following situations:

- If baseline measurements were  $<2 \times$  ULN, discontinue if ALT or AST increases to  $>5 \times$  baseline measurements.
- If baseline measurements  $\geq 2 \times$  ULN ( $\leq 200$  IU/L as per eligibility requirements), discontinue if ALT or AST increases to  $>3 \times$  baseline measurements.
- If baseline measurements  $\geq 5 \times$  ULN ( $\leq 200$  IU/L as per eligibility requirements), discontinue if ALT or AST increases to  $>2 \times$  baseline measurements.
- Discontinue if ALT or AST increase  $>2 \times$  baseline measurements AND the increase is accompanied by a concomitant increase in TBL to  $>2 \times$  baseline measurements or the INR concomitantly increases by  $>0.2$ , except for patients on anticoagulant treatment.
- For any patients who present with a constellation of syndromes indicative of liver disease as per the Investigator's overall assessment (i.e. fatigue, nausea, vomiting, right upper quadrant pain or tenderness, fever, rash, and/or eosinophilia [ $>5\%$ ]).

- **Close observation for suspected DILI includes the following:**

- Repeating liver enzyme (ALT, AST, and ALP) and TBL tests 2 or 3 times weekly. The frequency of repeat testing can decrease to once a week or less if abnormalities stabilize or the IMP has been discontinued and the patient is asymptomatic.
- Obtaining a more detailed history of symptoms and prior or concurrent diseases.
- Obtaining a history of concomitant drug use (including nonprescription medications and herbal and dietary supplement preparations), alcohol use, recreational drug use, and special diets.
- Ruling out acute viral hepatitis types A, B, C, D, and E; autoimmune or alcoholic hepatitis; hypoxic/ischemic hepatopathy; and biliary tract disease.
- Obtaining a history of exposure to environmental chemical agents.

- Obtaining additional tests to evaluate liver function, as appropriate (e.g. INR, direct bilirubin).
- Considering gastroenterology or hepatology consultations.

Only confirmed DILI should be reported as AESI.

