#### *8.3.8.4 Sponsor immediate notification and Regulatory Reporting*

##### *8.3.8.4.1 Sponsor Immediate Notification*

The Investigator must report immediately (within 24 hours of the Investigator's awareness) to POXEL as well as to Safety Provider all SAE/AESI/Overdose/Pregnancy occurring from

the date of ICF signature to the End-of-study Visit (V9-EoS) or to the last study visit performed in case of premature discontinuation.

For SAE, AESI, overdose and pregnancy, the study site must complete the corresponding eCRF page with as much available information within 24 hours of knowledge of the event.

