- treatment-related treatment-emergent serious AEs (TESAEs) by maximum severity (Grade 1, Grade 2, Grade 3, Grade 4, Grade 5)
- SAEs leading to death
- TESAEs leading to IMP treatment discontinuation
- TEAEs related to study procedures
- Treatment-emergent AESI's (Heart failure, Pitting edema, Bladder cancer, Bone fracture, Drug-induced liver injury – DILI)

The overview table will also summarize the number of events for the same categories in the Safety set.

Overview table for TEAEs will be repeated in the Safety set with site 065-S .

The number and percentage of patients reporting each pre-treatment AEs, TEAE, post-treatment AEs will be summarized by SOC and PT. Tables will be sorted by descending overall frequency of SOC. PTs will be sorted by descending overall total. The following summaries will be produced:

- Pre-treatment AEs, TEAEs, post-treatment AEs by SOC and PT
- TEAEs related to IMP treatment, by SOC and PT
- TEAEs causing discontinuation from IMP treatment, by SOC and PT
- TEAEs related to IMP treatment and causing discontinuation from IMP treatment, by SOC and PT
- TEAEs, by severity, SOC and PT
- Pre-treatment SAEs, TESAEs, post-treatment SAEs, by SOC and PT
- TESAEs related to IMP treatment, by SOC and PT
- Pre-treatment AEs, TEAEs, post-treatment AEs leading to death, by SOC and PT
- Pre-treatment AEs, TEAEs, post-treatment AESIs by SOC and PT

In the above summaries, patients with more than one AE within a particular SOC are counted only once for that SOC. Similarly, patients with more than one AE within a particular PT are counted only once for that PT. For summaries by maximum severity, patients with multiple AEs within a particular SOC or PT will be counted under the category of their most severe AE within that SOC or PT.

Additionally, the number and percent of each AE will be summarized for each treatment group, by descending overall frequency of SOC and PT (sorted by descending overall total), displaying the number of observed events for each PT.

Statistical Analysis Plan

Sponsor Name: Poxel
Sponsor Protocol ID: PXL065-003

TEAEs that are described as cardiovascular will also be summarized for each treatment group, by descending overall frequency of SOC and PT (sorted by descending overall total) displaying number of observed events for the Safety set.

Summary tables, will be repeated in the Safety set with site 065-S: for:

- TEAEs by SOC and PT
- TEAEs related to IMP treatment, by SOC and PT
- TESAEs by SOC and PT

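### No planned output counts, by arm, the patients who met the protocol's own liver stopping criteria: the DILI row waits for an undefined confirmation, and the elevation listing covers only part of the criteria

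*Protocol*

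**What the plan says.** Protocol 8.3.8.1.4 names DILI as one of five AESIs. AESIs, serious or not, follow the SAE process: "notification to the Sponsor within 24h following investigator awareness", plus a safety-database case with a narrative. Section 8.3.8.4.1 repeats the clock: "The Investigator must report immediately (within 24 hours of the Investigator's awareness) to" the sponsor and the safety provider.

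For the liver, the same section sets two groups of criteria, one for patients with normal baseline tests and one for patients with raised baseline transaminases or bilirubin. Each group has thresholds for repeat testing and close observation, and a list introduced by "Drug should be discontinued, and the patient followed until resolution of symptoms or signs in the following situations". Close observation includes "Ruling out acute viral hepatitis types A, B, C, D, and E; autoimmune or alcoholic hepatitis; hypoxic/ischemic hepatopathy; and biliary tract disease". The section then ends: "Only confirmed DILI should be reported as AESI".

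SAP 7.7.2 puts the treatment-emergent AESIs in the overview table, naming "Heart failure, Pitting edema, Bladder cancer, Bone fracture, Drug-induced liver injury", and gives no DILI definition of its own. SAP 7.7.3.1 plans a patient listing of ALT and AST above 3, 5 and 8 x ULN, total bilirubin above 2 x ULN, and ALP above 2 x ULN.

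**The concern.** An AESI category exists so that events of known interest reach the sponsor quickly and are counted in one place, whether or not they are serious. For the liver, the protocol defines in detail when a patient has gone far enough to stop drug, but meeting that definition does not make the event an AESI. The event becomes one only on confirmation, for which the protocol gives no criteria, decision-maker or deadline. The natural reading is that confirmation follows the exclusion of other causes, because that is the work-up described just before the rule; the text does not say so outright.

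At stake is the randomized comparison. In a placebo-controlled trial, the arms can be compared on how many patients met an objective criterion, with no case-by-case attribution. If the only row labelled DILI depends on an undefined judgement, it can show no cases although patients met stopping criteria, and the reader has no table that says otherwise.

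**Working it through.** The plan states no figure to reproduce. The check sets the reporting routes, and then the criteria and outputs, side by side.

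**1. Reporting routes for an unconfirmed case that meets a stopping criterion**

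| Route | Starts when | Timing | Enters the DILI row? |
|---|---|---|---|
| AESI (Protocol 8.3.8.1.4, 8.3.8.4.1) | DILI is confirmed | 24 hours | Yes |
| SAE (8.3.8.1.3, 8.3.8.4.1) | A seriousness criterion is met, including medically important | 24 hours | Not unless confirmed |
| Ordinary AE (8.3.6 and the paragraph on abnormal laboratory findings) | Finding is clinically significant, symptomatic, leads to drug stop, or is medically important | eCRF entry within 5 business days of the visit (11.1) | Not unless confirmed |
| Withdrawal notice (5.8.2) | Patient withdraws | Immediate, to medical monitor and sponsor medical representative | No |

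So the case is visible to the sponsor. What it lacks, when non-serious and unconfirmed, is the 24-hour AESI case, the narrative and a place in the DILI row.

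**2. Stopping criteria against the SAP listing**

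Inputs: criteria from Protocol 8.3.8.1.4; listing limits from SAP 7.7.3.1. Let b be the baseline transaminase and t the baseline bilirubin, both in x ULN.

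- *Normal baseline.* Every criterion needs ALT or AST above at least 3 x ULN, so these patients are listed. The listing has no entry for the parts that complete a criterion: more than 2 weeks above 5 x ULN, coincident bilirubin, INR above 1.5, or symptoms.
- *Raised baseline, transaminase alone.* For an enzyme that was itself raised: b above 1 and below 2 gives 5b > 5; b at least 2 gives 3b ≥ 6; b at least 5 gives 2b ≥ 10. All exceed 3 x ULN, so the patient is listed, but not identified as meeting a criterion. If the enzyme that rises was normal (assumed b = 0.5, with another liver index raised), the criterion is 5 × 0.5 = 2.5 x ULN, below the listing limit of 3.
- *Raised baseline, combined.* The criterion is transaminase > 2b with bilirubin > 2t. It escapes the listing when 2b < transaminase ≤ 3 and 2t < bilirubin ≤ 2, which is possible when b < 1.5 and t < 1. Assumed example: b = 1.2 and t = 0.5 give limits of 2.4 and 1.0. Values of 2.5 and 1.1 are 2.5/1.2 = 2.08 and 1.1/0.5 = 2.2 times baseline, so the criterion is met. Both lie below the listing limits of 3 and 2; with AST and ALP also below their limits, the patient is not listed.
- *INR and symptom criteria.* The INR rise of more than 0.2 can replace bilirubin in the combined criterion, and INR is not in the listing. The criterion based on symptoms has no counterpart there.

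**3. Outputs by arm**

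- DILI row (SAP 7.7.2): confirmed cases only.
- TEAEs leading to discontinuation, by SOC and preferred term (SAP 7.7.2): includes stopped cases reported as AEs, under whatever condition was recorded. It does not group them by liver criterion, and it omits a patient who met a criterion but was not stopped.
- Laboratory summaries by visit (SAP 7.7.3.1): under SAP 6.1 an unscheduled value stands in for a visit only when the scheduled one is missing, so the repeat test after 48 to 72 hours would often not enter.
- MMRM for liver enzymes (SAP 7.6.2.3): compares mean changes, not patients above a limit.
- Elevation listing: sorted by treatment group (SAP 7.1), so a reader could count its entries by hand, but only the entries it has.

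None of these counts patients by stopping criterion and arm.

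**4. Scale, as an illustration only**

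The documents give no rate. With the planned 3 × 30 = 90 patients on active drug, suppose 2 met a criterion and neither was confirmed. The DILI row shows 0/90; the exact 95% upper limit is 1 − 0.025^(1/90) = 4.0%. A count by criterion shows 2/90 = 2.2%, exact 95% interval 0.3% to 7.8%. The counts are invented for scale, and the Safety Set excludes one site, so the true denominator differs.

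**The case against.** The strongest reply is that the sponsor learns of these cases anyway. A reader might infer that a serious liver signal arrives late or never. The documents do not support that. For a patient with normal baseline tests, ALT above 3 x ULN with bilirubin above 2 x ULN is itself a stopping criterion, and a finding that leads to drug stop is a reportable AE. The paragraph that begins "Abnormal laboratory findings and other abnormal investigational findings (e.g. on an ECG tracing) should not be reported as AE unless" makes that exception, and Protocol 8.3.6 separately requires AE reporting of clinically significant laboratory findings. Withdrawal is notified immediately, and a case judged medically important is an SAE with its own 24-hour clock. The study-pause rule in 5.9 works from CTCAE grade and relatedness, not AESI status. All of this stands.

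A reader might also contrast DILI with the heart failure entry: "Heart failure. In case of any event of heart failure, whatever the cause, patients should be referred to a cardiology specialist". The words about cause there govern referral to a cardiologist, not reporting, so the contrast proves nothing.

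DILI is by name a causal diagnosis, so a row that requires attribution is legitimate. That is a reason to keep the confirmed row and set an attribution-free count beside it. An adverse event reporting plan that is not part of these documents (Protocol 11.1) may define confirmation; if so, the protocol should point to it.

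Finally, making every persistent elevation an AESI would be too wide. Under the raised-baseline rules, bilirubin moving from an assumed 0.3 to 0.7 mg/dL and staying there exceeds twice baseline, although it is below the entry limit of 1.3 mg/dL. That extension is not proposed.

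**Conclusion.** The point holds in a limited form. A non-serious case that meets a liver stopping criterion generates no 24-hour AESI report or narrative before an undefined confirmation, and the SAP's DILI row counts confirmed cases only. No planned output counts by arm the patients who met the criteria. The listing that is free of causality judgement covers single parameters in multiples of ULN; it does not identify the baseline-relative, combined or INR criteria, and some patients who meet them do not appear in it at all.

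This is a gap in tabulation and in the reporting channel. It is not evidence that the sponsor would be unaware. The length of any delay in AESI reporting cannot be derived, because the protocol sets no time for the work-up. The conclusion rests on reading the SAP's DILI row as taking the protocol's definition, which follows from the SAP having none of its own. The improvement is cheap and worth making.

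**What to change.** 1. **SAP 7.7.2 and 7.7.3.1.** Add a table by arm, Safety Set, of patients meeting each laboratory-based liver discontinuation criterion of Protocol 8.3.8.1.4, including the baseline-relative, combined and INR criteria, and patients meeting any of them. Place it next to the confirmed-DILI row. State that all post-baseline values count, scheduled and unscheduled, and say how local results are treated, since SAP 7.7.3.1 only lists them. This uses data already collected and costs one derivation and one table.
2. **Protocol 8.3.8.1.4.** Replace the closing sentence with a rule that a patient meeting a liver discontinuation criterion of that section is reported within 24 hours as an AESI of *suspected DILI*, and that confirmed or not confirmed is added at follow-up. Define confirmation and who makes it. Do not extend the trigger to every persistent elevation.

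No clinical threshold changes. The downside is a few more notifications and narratives for events that prove to have another cause, and an amendment for item 2. The SAP is dated 12 August 2022, after the planned study end of Q1 2022. If treatment is already complete, item 2 can serve only later studies; item 1 can still be done, labelled as an addition and, if the blind is broken, as post hoc.
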